Attention has recently turned toward using smartphone applications (apps) to improve health behaviors.[16] Such technology extends healthcare beyond in-person clinical visits due to its versatility, portability, and potential cost-savings. However, *few health apps are scientifically evaluated[17-19] and even fewer are tailored to the specific needs of older adults.* This research gap has prompted the Centers for Disease Control to call for studies that link mobile health (mHealth) solutions to healthy aging agendas.[20]

In the proposed study, we will develop, test, and optimize a core app and set of attached specialty features that are designed to facilitate older adults’ PA. This package, termed the *Moving Up* suite, is distinct from generic fitness apps because it blends evidence-based behavior change techniques (e.g., self-regulation via activity monitoring) in the core app with a set of specialized components that reflect empirically supported constructs from social cognitive[21, 22] and stereotype embodiment theory.[23] Specialty features include: (a) implicit and explicit messaging to promote positive aging views; (b) sedentary activity (SA) monitoring with motivational messaging and peer suggestions; and (c) data-driven, automated remote coaching and support. *To date, no other app has offered a comparable suite that has been systematically optimized to address inactivity in older people, justifying the need to scientifically evaluate this type of tool.* In the clinical trial phase of the study, we will utilize a highly efficient, innovative methodological approach—Multiphase Optimization Strategy (MOST)[24, 25]—to provide an experimental context for evaluating each of the *Moving Up* suite’s specialty features. The MOST procedure originated from the field of engineering and is explicitly designed to facilitate selection of intervention components by elucidating their individual and synergistic effects (a key gap in health app research).

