
A.2. Clinical Trial Design Details

We will utilize the MOST procedure to assess the app suite specialty features’ efficacy and other performance aspects. MOST is explicitly designed to disentangle the effects of multiple components that make up an intervention^{26,105}—a key project goal given our intent to appraise the merit of novel, previously untested app features. Traditionally, multi-component interventions are subjected to efficacy pilot tests followed by large RCTs, but in the absence of systematic evaluations of singular components. However, in such cases: (a) the intervention may contain inert ingredients that contribute to subpar or cost-inefficient results; or (b) difficulties may arise in determining which intervention aspects contribute to efficacy, due to the presence of multiple components which have not been individually tested. In contrast, following

[figure not shown]

Figure 2. Theoretical Framework for the PA-tracking App Suite. SCT=Social Cognitive Theory; SET=Stereotype Embodiment Theory; PA=Physical activity; SA=Sedentary Activity

systematic optimization as facilitated by MOST, subsequent RCTs are expected to produce sharper, more interpretable results.

Based on recommendations from the MOST literature, we will employ a 2x2x2 factorial experiment in which three between-subject factors, corresponding to the presence vs. absence of each specialty feature, will be manipulated in a completely crossed design, given each participant's utilization of the core app. Following random assignment (using a computer algorithm designed for this purpose) to the eight conditions, participants will undergo a four-month intervention interval. Experimental outcomes will consist of pre-to-post change scores on PA-related and mediating variables, and documentation will also be provided for parameters such as usage frequency and user satisfaction that are pertinent to subsequent efforts to achieve optimization.

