Each specialty feature will be provided to half of the participants, leading to respective comparative assessments that involve 45 vs. 45 (feature present vs. absent) participants. Accordingly, it is incorrect to conceptualize this design as a test of outcome differences between eight separate inadequately powered cells; rather, the intent is to collapse information across cells so as to obtain a reasonably large sample size when examining each component's performance.[24] Further, because the specialty features would be inexpensive to download if used in large-scale distributions of the app, and because they have been carefully designed to reflect empirically supported theory, it is important to avoid premature elimination of features on the basis of non-significant experimental effects which in actuality may stem from sample size limitations. Consequently, in evaluating intervention components we will downplay the importance of (though still include) significance testing of PA outcomes, and instead will incorporate the total array of relevant information (e.g., effect sizes, usage rates, satisfaction ratings) in the final component selection and fine-tuning process.

B. Participants, Recruitment, and Consent

For Aim 1, a convenience sample of 15 elders will be recruited from independent-living communities within FPCIW's 2,000-member senior network in Los Angeles (LA) and local senior venues. An estimated 1,300 FPCIW members use smartphones.[45] Iterative phases of product development require only five to seven representative users per prototype iteration,[46] justifying our sample size of 15 (five per app suite specialty feature).

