Our biostatistician will secure and archive data, and will oversee all data analytic functions. Usage data for each participant will be obtained from storage within the app and downloaded manually at in-person assessment sessions. Data will be transferred to the biostatistician for analysis and storage on the USC secure network. activPAL data will be downloaded and cleaned. Using proprietary algorithms supplied by PAL Technologies, waking-hour wear periods will be identified for use in analysis.

Data analysis will be organized around the goal of providing multiple sources of information useful for future efforts to optimize the Moving Up app suite. We will calculate *descriptive statistics* at baseline and/or post-intervention for demographic, *app usage behavior* [proportion of days opening the app ≥ 1 time], *user satisfaction* [perceived app quality, physical activity-related (*objective physical activity* [primary outcome; daily steps], *sedentary activity time* [daily sitting time], *self-reported physical activity*, *functional mobility* [gait speed]), and mediational (i.e., *self-efficacy for physical activity*, *self-regulation for physical activity*, *family social support for physical activity*, *outcome expectation for physical activity*, *aging self-perceptions*, *views of aging*) outcome variables, both for the overall sample and by on/off status of each of three specialty features (i.e., Proof Positive, Coach Me, and On Your Feet).

Indicator variables will be created to code whether or not the participant had each of the specialty features installed on their phone as part of the intervention. Results regarding outcomes and hypothesized mediators will be calculated overall and by feature subgroup. The feature subgroups are not mutually exclusive since a participant can be randomized to receive 0, 1, 2, or all 3 of the features.

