Specialty feature condition effects on the *objective physical activity* (change in daily steps) primary outcome will be analyzed using a mixed effects linear regression model adjusted for confounders (including presence/absence of other specialty features, between-feature interactions, select demographic variables [age, sex, race/ethnicity, education]), and baseline daily steps. Although significance testing will provide merely one source of information in driving app optimization decisions, the anticipated sample size (N=90) was chosen to enable 80% power (given $\alpha=.10$ and a one-tailed test, as consistent with recommendations for pilot studies employing MOST) in testing experimentally based pre-post physical activity increases associated with a specialty feature (given an effect size of .45, a feasible value based on prior tests of technology-based physical activity intervention components). Using change-from-baseline scores for *objective physical activity*, we will derive Cohen's *d* effect sizes stratified by presence vs. absence of each specialty feature. For secondary physical activity-related outcomes and proposed mediators, we will conduct multiple one-tailed t-tests ($\alpha=.10$) to further explore the potential viability of the specialty features. To facilitate later RCT planning, we will also calculate single group pre-post change effect sizes for the full sample. Correlation coefficients will be calculated to assess associations between the primary outcome (change in daily steps) and proposed mediators. To analyze *app usage behavior* and *user satisfaction*, for each intervention feature considered separately, we will perform one-tailed t-tests to examine mean differences in each variable based on whether or not the participant was assigned to receive that feature.

After participants conclude the clinical trial phase, they will take part in an interview about their experience. Interview responses will be audio-recorded, transcribed verbatim, coded, and analyzed using qualitative data analysis software. All qualitative data analyses will be performed by the PI, Co-investigators, and/or authorized Research Assistants. Initial thematic analysis will incorporate codes suggested from the Health-ITUDEM.[71] Additional codes will be identified as they arise in the data. Rigor will be achieved through peer review of themes and by maintaining an audit trail of analytic memos.

IV. Protection of Human Subjects

A. Risks to Human Subjects

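### The plan cites synergy as a reason for the factorial design, but no planned quantitative analysis of usage or satisfaction can show how features combine, and the steps-model interactions have no stated estimand or reporting

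*Combined protocol and SAP*

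**What the plan says.** The introductory section, before II. Approach & Methods, says that the optimisation framework is designed to "facilitate selection of intervention components by elucidating their individual and synergistic effects". Section II.A.2 sets the design: "we will employ a 2x2x2 factorial experiment in which three between-subject factors", fully crossed. It then puts the weight on one-feature comparisons, "leading to respective comparative assessments that involve 45 vs. 45 (feature present vs. absent) participants", and explains that "the intent is to collapse information across cells so as to obtain a reasonably large sample size". The same section plays down significance tests of activity outcomes. It names effect sizes, usage rates and satisfaction ratings among the inputs to the final choice and refinement of components.

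Section III then sets the analyses:

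- **Steps (primary).** A mixed effects linear regression includes between-feature interactions, but lists them among the confounders to adjust for. Their order (two-way or three-way), estimand, scale and reporting are not stated. Cohen's d is derived only by presence or absence of each feature.
- **Usage and satisfaction.** "for each intervention feature considered separately, we will perform one-tailed t-tests to examine mean differences in each variable", according to whether the participant was assigned that feature.
- **Secondary outcomes and mediators.** One-tailed t-tests at 0.10, with no interaction term.
- **Descriptive summaries.** "both for the overall sample and by on/off status of each of three specialty features". The section notes that a participant may have none, one, two or all three features, but plans no summary by combination.

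**The concern.** A crossed design produces the data needed to see whether features help or hinder one another. On usage and satisfaction the plan leaves that information unused, although both feed component selection. A present-versus-absent difference averages over the other two features. It can be zero, or favour a feature, when the result depends on what else is switched on.

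Interference is plausible from section II.A.1: Proof Positive sends texts, On Your Feet sends reminders, tips and messages, and Coach Me sends daily messages. The documents do not name message overload as a concern, so this is an inference from the feature descriptions. If features did compete for attention, usage and satisfaction are natural places to look. The planned one-feature tests could not attribute a change to a combination.

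For steps the gap is smaller. The interaction coefficients will be estimated, but nothing says what they mean or that they will be shown.

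**Working it through.** **Inputs.** Analysed N = 90, that is 100 × (1 − 0.10), from sections II.B and III; 45 against 45 per feature (II.A.2); eight conditions, so 90/8 = 11.25 per cell if balanced; α = 0.10 one-tailed, effect size 0.45 SD and 80% power (III). The documents give no interaction size, so those below are assumptions. Outcomes are in SD units, with the normal approximation.

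**1. The plan's own figure.**
SE of a present-versus-absent difference = √(1/45 + 1/45) = 0.211.
Power = Φ(0.45/0.211 − 1.2816) = Φ(0.853) = 80.3%.
The stated 80% reproduces. It applies to one feature's main effect on steps and to nothing else.

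**2. What a one-feature comparison can miss.** Assume mean satisfaction of 0, 0.40, 0.40 and 0 SD with none, one, two and three features, in equal cells.

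- Feature on (one single-feature cell, two two-feature cells, one three-feature cell): (0.40 + 2 × 0.40 + 0)/4 = 0.30.
- Feature off (core only, two single-feature cells, one two-feature cell): (0 + 2 × 0.40 + 0.40)/4 = 0.30.
- Difference = 0 for all three features, so each planned t-test rejects only at its 10% α.
- Two-way interaction, averaged over the third feature: both on 0.20, first only 0.40, second only 0.40, neither 0.20. Difference in differences = 0.20 − 0.40 − 0.40 + 0.20 = −0.40 SD.

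The whole pattern sits in the interactions.

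**3. A pattern that does reach the marginal means.** Assume a fall of 0.90 SD in the all-three cell only. Each marginal difference is −0.90/4 = −0.225 SD. A one-tailed test for benefit would reject with probability Φ(−0.225/0.211 − 1.2816) = 0.9%, and one for harm with Φ(0.225/0.211 − 1.2816) = 41.5%. The plan does not state which tail applies. In either case the fall would be spread across three features and not traced to the combination.

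**4. How precise the missing estimates would be.** A difference in differences compares four groups of 22.5:
SE = √(4/22.5) = 0.422 SD, twice that of a main effect.

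| True difference in differences | One-sided power, α = 0.10 |
|---|---|
| 0.225 SD | 22.7% |
| 0.40 SD | Φ(0.40/0.422 − 1.2816) = 37% |
| 0.45 SD | 41.5% |
| 0.90 SD | 80.3% |

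The size detectable with 80% power is 0.422 × (1.2816 + 0.8416) = 0.90 SD.

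With −1/+1 coding every coefficient has the same SE, 1/√90 = 0.105. That does not make interactions as easy to detect as main effects: a difference in differences of 0.40 is then a coefficient of 0.40/4 = 0.10, while a main effect of 0.45 is 0.45/2 = 0.225. The power does not depend on the scale.

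**5. Effect on the planned comparisons.** With effect coding and equal cells the terms are orthogonal, so adding the interactions leaves the main-effect difference and its SE of 0.211 unchanged.

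**The case against.** The strongest objection concerns purpose. The sentence about synergy describes the optimisation framework in general. The specific aim is a screening pilot that examines each feature, and section II.A.2 defends the factorial design by collapsing across cells. On that view, joint effects were never this trial's target. This has force and limits the severity. It does not remove the point: the plan presents synergy as something its method reveals, puts interactions in one model without saying what will be done with them, and uses usage and satisfaction for selection.

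A reader might go further and infer that interference between features would go entirely undetected. The documents do not support that. The steps model estimates interactions. Check-in calls in months 1 to 3 gather impressions of app use (IV.A.1), a post-trial interview is coded and analysed thematically (III), and step 3 shows that some patterns lower the marginal means. Participants also control reminder frequency in On Your Feet and how much they use any feature.

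A reader might also infer that the fix would reliably detect interference. It would not. A contrast picked to match the assumed pattern, such as one or two features against none or three, would look better powered, but only because it was fitted to that pattern. The individual interactions have the power shown in step 4. Means by number of features alone would also be a poor summary, because they treat the features as interchangeable and cannot show which pair does best.

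Finally, cells of about 11 people invite choices driven by noise. That stands, and is the reason for the exploratory label. Low power does not justify omission, since section II.A.2 itself declines to let significance decide.

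**Conclusion.** The point holds as a gap in analysis and reporting. No planned quantitative analysis or table of usage or satisfaction, or of secondary outcomes and mediators, can show how features combine. The steps-model interactions have no stated estimand or reporting. The plan should be amended, but the planned main-effect comparisons and their stated power are unaffected.

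The size is conditional. Under the assumed 0, 0.40, 0.40, 0 pattern all three marginal differences are exactly zero while each two-way interaction is −0.40 SD. With N = 90 such an interaction would be estimated with an SE of about 0.42 SD and found with about 37% one-sided power. These figures assume equal cells, 10% attrition spread evenly, unit SD and approximate normality. Usage is a proportion of days, so normality is only rough there. Neither the existence nor the size of any interference is established by the documents.

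**What to change.** - **Usage and satisfaction.** Replace the separate t-tests with one linear model per outcome containing the three features, coded −1/+1, and their three two-way interactions. Baseline smartphone proficiency, already collected in Table 1, may be added as an optional covariate.
- **Steps.** State the same coding and the order of the interactions, and describe them as estimands, not confounders. Coding matters here because section III says only that indicator variables will be created. With 0/1 coding and two-way terms, a feature's coefficient is its effect with the other features off, with SE √(12/90) = 0.365 and power for 0.45 SD of 48.0%, against 80.3% with effect coding.
- **Reporting.** For all three outcomes, report main effects, the two-way interactions as differences in differences with two-sided intervals (interference would be a harm), and model-based means for the eight combinations with the number of people in each.
- **Use.** Label these results exploratory, and list them in section II.A.2 as supporting information for component selection. Claim no power for them.

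The cost is SAP wording and one extra table, with no new participants or data. The downside is imprecision: a 95% interval for an interaction extends about 1.96 × 0.422 = 0.83 SD either side. The model-based means also assume no three-way interaction, which 90 people can hardly check.

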The PA-tracking core app mainly targets self-regulation and outcome expectation. Its goal-setting function submits a default, adjustable daily PA benchmark. By displaying real-time PA, it allows visual tracking of goal progress. In addition to the core app, three specialty features are proposed that also address key SCT or SET considerations and are tailored to overcome elder PA barriers: **(1) Proof Positive**, as motivated by SET, capitalizes on the beneficial effects that exposure to positive aging messages and stereotypes have on health and PA.[29, 33] When activated, users (a) receive texts describing how old age does not equate to physical inability, (b) obtain information about the benefits of growing older, and (c) are presented with a variety of positive aging stereotype tasks modeled after priming activities commonly used in the field (e.g., word scrambles,[34] picture identification,[35], computerized series [33, 36-38]). This last example exposes users to blocks of “positive priming words”.[33] Primers are quickly flashed to allow perception without awareness[36] while users focus on an image of activity—a step that builds on Levy’s work by simultaneously offering explicit cues that promote PA. **(2) On Your Feet** is designed to reduce SA—a health risk factor largely independent of insufficient PA[39]—by using self-regulatory and behavior change techniques including goal-setting, progress feedback, and prompting.[40] Accumulated sedentary time is displayed alongside self-selected goals; audible, vibratory, or text-based reminders to stand are sent at a user-specified frequency; and general tips as well as previously compiled, older adult-identified strategies to reduce SA[6] are texted. Additionally, messages about the benefits of reducing SA and overcoming barriers (e.g., fatigue) are also sent. **(3) Coach Me** includes daily messages designed to assist older adults in (a) discovering practical ways to integrate brief bouts of PA into their daily routines and (b) overcoming common PA barriers.[41, 42] Blending PA with productive activity has been identified as a key facilitator of PA engagement in older people.[43, 44] In *Coach Me*, suggestions on how to intensify common daily activities are tailored based on user selections from an activity inventory stored within an individual’s *Moving Up* profile. For example, if a user identifies “laundry” on the inventory, *Coach Me* may suggest “heel raises while holding onto the dryer before placing clothing in a basket.” This app feature is intended to help older adults become more active in a minimally intrusive way, while allowing for simultaneous engagement in productive and meaningful activities. *Coach Me* asks users to select obstacles to PA encountered in the previous week. Based on those selections, the app sends strategies on how to overcome those barriers in the future, thereby targeting self-efficacy.

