One-hundred community-living older adults who are served by Front Porch Center for Innovation and Wellbeing (FPCIW) will be primarily recruited from FPCIW's 2000-member senior network in Los Angeles. FPCIW will facilitate recruitment, referring its eligible members to the study team. Justification for the targeted sample size is multifold. First, an adequate number of participants will be available to enable meaningful analyses (final N=90) given a four-month attrition rate of 10% (estimate based on averaging interval-adjusted study completion rates in five studies of mHealth or web-based PA interventions for adults aged >40 years[47-52]. Second, the expected overall (N=90) and per-feature (n=45) sample sizes well exceed the number of participants previously described as necessary to determine if a larger trial is warranted.[53] Third, the stipulated sample size is easily achievable and represents roughly the maximum number of participants attainable given available funding resources.

Persons will be deemed eligible based on the following criteria. Inclusion criteria: men or women, 65–84 years old; English speaking; reside in LA or in Pacific Time Zone if participating remotely; score ≥ 5 on a 6-item cognitive screener[54]; report <150 minutes of moderate-to-vigorous PA/week as per a single-item screener;[55] ambulatory; ability to safely participate in PA as determined by self-report of ability to regularly walk safely; smartphone owner for ≥ 1 month; observed ability to reliably access and operate a smartphone during orientation; available by telephone for the duration of either study. Exclusion criteria: unwillingness to meet at local community venues and/or via online meetings to comply with study procedures for the length of each study. Although not an eligibility criterion per se, access to a computer and webcam, and sufficient computer skills to participate in virtual orientation is necessary if in-person orientation is not feasible.

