A.1. Human Subject Involvement, Characteristics, and Design

A total of 100 underactive older adults (accounting for 10% attrition) will participate in the clinical trial phase to accomplish the aims of the study. Subjects will be between the ages of 65 and 84 years old, and will be users of smartphones for ≥ 1 month. Underactive individuals will be targeted (i.e., those who accumulate <150 minutes of at least moderate intensity physical activity per week) due to their high risk for chronic disease resultant from lack of physical activity engagement and sedentary behavior. Additional inclusion criteria for entrance into the study includes ability to reliably access and operate basic features of a smartphone (ascertained by completion of the two-hour orientation and demo session). Exclusion criteria are unwillingness to meet at local community venues or comply with study procedures for the length of each study.

A four-month intervention period will take place. On a randomized basis, the research participants (N=100) will be assigned to one of eight conditions whereby they will have access to various combinations of the app suite features. Intervention dosage is consistent with small pilot studies of physical activity interventions for older groups of adults. They will complete an orientation session, either in person or online. Check-in phone calls will be made by project staff during months 1, 2, and 3, for purposes of troubleshooting and gleaning initial impressions of app usage. A short interview covering usability and feasibility will be conducted during the final phone check-in just after completion of the 4-month intervention. Pre- and post-intervention, each participant will complete a battery of self-report assessments and clinical measures and complete a three-day physical activity monitoring period using a wearable accelerometer. These assessments will be either (1) mailed to participants or dropped off/picked up

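### Nothing stops two members of one household enrolling, and individual randomisation would split them on a given feature half the time; one member per household is a cheap safeguard

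*Combined protocol and SAP*

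**What the plan says.** - **Unit of randomisation.** Section IV.A.1 states: "On a randomized basis, the research participants (N=100) will be assigned to one of eight conditions". Section II.A.2 describes the design as one in which "three between-subject factors, corresponding to the presence vs. absence of each specialty feature, will be manipulated in a completely crossed design". Each feature is judged on a comparison of "45 vs. 45 (feature present vs. absent) participants".
- **Eligibility.** Section II.B gives as its only exclusion: "Exclusion criteria: unwillingness to meet at local community venues and/or via online meetings to comply with study procedures for the length of each study". The inclusion list there and the summary in section IV.A.1 are also silent on cohabitants.
- **Recruitment.** Participants "will be primarily recruited from FPCIW's 2000-member senior network in Los Angeles". Section IV.B.1 adds telephone contact from the partner organisation's database and talks at affiliated senior centres or outside networks.
- **Content.** Under On Your Feet (section II.A.1), "audible, vibratory, or text-based reminders to stand are sent" at a frequency the user sets, and tips are texted. Coach Me draws its suggestions from the user's own activity inventory and reported barriers. Proof Positive combines texts and information with on-screen tasks, including primes flashed too briefly to be consciously noticed.
- **Household data.** Table 1 lists marital and living status for description and as possible covariates. Neither shows whether a partner is also in the trial.
- **Use of results.** Section II.A.2 gives significance tests a reduced role and selects components on effect sizes, usage and satisfaction together.

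**The concern.** Telephone contact from one network's database and talks at senior centres can reach both members of a couple, and the plan does not say what happens if both qualify. Randomised separately, they will often differ on a feature. Some content can cross a living room: an audible cue, a tip read aloud, a suggestion tied to a household chore. A participant counted as feature-absent would then be partly exposed.

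If the feature works and its content is shared, the difference between the present and absent groups shrinks. The estimate itself is biased, so giving less weight to p-values does not remove the problem. The stake is that a useful feature looks weaker than it is, in a trial that explicitly wants to avoid dropping features too early.

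**Working it through.** **Inputs from the documents.** 45 vs 45 analysed (section II.A.2); effect size .45, alpha .10, 80% power (section III), "and a one-tailed test, as consistent with recommendations for pilot studies employing MOST".

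**Step 1: reproduce the plan's figure.** Noncentral t with 88 degrees of freedom and noncentrality .45 × √(45/2) = 2.13, one-sided .10, gives power 80.0%. The normal approximation gives 80.3%. The stated 80% reproduces, with almost no reserve.

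**Step 2: chance that partners differ.** With independent, equal allocation:
- on any one feature: 1/2 (50/99 = .505 if 100 people are split exactly 50:50);
- on at least one of three features: 1 − 1/8 = 7/8.

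Each contrast concerns one feature, so 1/2 is the figure that matters.

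**Step 3: dilution.** Let *h* be the share of participants with a co-enrolled partner and *c* the fraction of the feature's effect that passes to a partner without it. The documents give neither; both are assumptions. A feature-absent participant has a partner with the feature with probability *h*/2, so

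observed d = .45 × (1 − *h* × 0.5 × *c*).

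Example: *h* = 20%, *c* = 50% gives .45 × (1 − .05) = .4275.

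| In couples (*h*) | *c* = 10% | *c* = 25% | *c* = 50% | *c* = 100% |
|---|---|---|---|---|
| 10% | .448, 79.7% | .444, 79.3% | .439, 78.5% | .427, 76.9% |
| 20% | .446, 79.4% | .439, 78.5% | .427, 76.9% | .405, 73.6% |
| 30% | .443, 79.1% | .433, 77.7% | .416, 75.3% | .383, 70.0% |

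Each cell shows observed d and power (noncentral t, 45 vs 45, one-sided .10). With *h* = 0 the figures stay at .45 and 80.0%. At *c* = 10% to 25% the loss runs from 0.3 to 2.3 points; at *c* = 50%, from 1.5 to 4.8 points. The last column is an upper bound, not an expectation.

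**Step 4: does correlation between partners do harm of its own?** A simulation with 18 of 90 people in couples compared the variance of one feature contrast with its value for unrelated people. Within-pair correlations of 0.2 and 0.5 are assumptions.
- Individual randomisation: ratio about 1.00 and 0.99. Pairs that agree on the feature and pairs that differ cancel.
- Both partners given the same condition: ratio about 1.05 and 1.10, close to the approximation 1 + 0.20 × correlation = 1.04 and 1.10.

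The clustering penalty therefore arises only if couples are allocated together. Using the approximation, joint allocation would give power of 78.9% (correlation 0.2) or 77.2% (correlation 0.5), against 76.9% for leaving the design alone with *h* = 20% and half the effect shared. It loses power overall if the fraction shared is below about 19% or 46% respectively.

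**The case against.** The strongest reply is that the premise is hypothetical. The documents never mention couples or cohabitants. Both partners would have to be 65 to 84, underactive, smartphone owners, pass the cognitive screener and volunteer. Recruitment also extends to remote participants in the Pacific Time Zone and to outside networks. This stands: the number of couples could be zero, and then there is no effect.

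The second reply is that most content is personal. It runs on the user's own phone; On Your Feet also depends on the user's own sedentary display and goals; Coach Me is tailored to one profile; and a bystander would hardly receive subliminal primes. This also stands. A reader might infer that all three contrasts are pulled toward zero. The feature descriptions do not support that: spillover is most plausible for On Your Feet, weaker for Coach Me, and slight for the primes in Proof Positive.

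The third reply is that the shift is small. A change from .45 to between .44 and .42 is well inside the sampling error of d, about √(2/45) = 0.21, in a pilot that does not decide on significance alone. That is correct, and it is why the point is minor. But sampling error does not cancel a bias, and this one can be avoided at almost no cost.

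**Conclusion.** The gap is real but minor. The eligibility criteria permit two people from one household, and individual randomisation would put them on opposite sides of a given contrast half the time. If couples enrol, share content and the feature works, the affected effect sizes are biased modestly toward zero: .45 appears as .44 to .42, with power of about 79% to 75%, if 10% to 30% are in couples and half the effect is shared. With 10% to 25% shared the loss is about 0.3 to 2 points. With no couples it is nil. The couple share and the fraction shared are assumptions throughout.

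Two stronger readings are not supported. A reader might take the 7/8 chance of different conditions as the degree of exposure, but for any single contrast the figure is 1/2. A reader might also infer that correlation between partners' step counts, with no household term named in the model, undermines the planned analysis. Under individual randomisation it does not inflate the variance of a feature contrast (Step 4).

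This is a cheap improvement to the design.

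**What to change.** Ask at screening whether another member of the household has enrolled or is being screened, and add to the eligibility criteria in section II.B, with the matching summary in section IV.A.1: *Only one member of a household may be enrolled in the clinical trial phase.*

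The cost is one screening question and a few volunteers turned away, to be replaced from the network; section II.B itself describes the target of 100 as readily reached. If no couples volunteer, the rule costs nothing. If they do, it removes sharing between co-enrolled partners without a clustering penalty.

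If cohabitants have already been enrolled, record which participants share a home and add to section III a sensitivity analysis for each feature that excludes pairs who differ on that feature.

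Giving both partners the same condition, with a household random effect, is not the preferred remedy. It creates the variance penalty in Step 4, can reveal the second partner's assignment before that person enrols, and would estimate the household effect from few pairs (nine if 20% of 90 are in couples).
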